## 1 INTRODUCTION

### 1.1 STATEMENT OF INTENT

The design, conduct and reporting of this trial shall be conducted in compliance with the protocol, International Conference on Harmonization (ICH)/Good Clinical Practice (GCP) and all appropriate regulatory requirements. The protocol will follow 21 Code of Federal Regulations (CFR) 50, subpart D and will provide all the necessary safeguards for study subjects. All of the Investigators will have documented training in GCP. Independent monitoring of the trial will be accomplished by utilizing a Contract Research Organization (CRO).

### 1.2 STUDY BACKGROUND

Atopic Dermatitis (AD) is a chronic, pruritic inflammatory skin disease of unknown origin that usually starts in early infancy, but also affects a substantial number of adults. AD affects 15-30% of children and 2-10% of adults globally, and its prevalence rate is rising (Alhazmi, 2017). AD onset is most common between 3 and 6 months of age, with approximately 60% of patients developing the eruption in the first year of life and 90% by 5 years of age (Kay, 1994; Perkin, 2004). While the majority of affected individuals have resolution of disease by adulthood, 10% to 30% do not, and a smaller percentage of individuals first develop symptoms as adults (Ellis, 2012).

AD is often associated with elevated serum immunoglobulin (IgE) levels and a personal or family history of type I allergies, allergic rhinitis, and asthma (Eichenfield, 2014). AD typically presents with pruritus, xerosis, lichenification, and eczematous lesions. Excoriations and crusting are common and some patients exhibit prurigo nodularis-like lesions. The eczematous changes and its morphology are seen in different locations depending on the age of the patient. In adults, lesions are more diffuse with an underlying background of erythema. The face is commonly involved and is dry and scaly. The mainstays of treatment are moisturization (frequent lukewarm baths, and using petrolatum or Aquaphor, etc.), along with topical steroids (Eichenfield, 2014). For more severe cases, other treatment options such as immunomodulators (ex. tacrolimus and pimecrolimus), biologicals (ex. dupilumab and omalizumab), topical phosphodiesterase-4 (PDE-4) inhibitors (ex. crisaborole), probiotics and phototherapy are also used (Sidbury, 2014). All of these options for AD management, and many of these treatment regimens are considered expensive and with various side effects in chronic use. Thus, patients with AD are in need of new treatment options that are efficacious and safe in the long term use.

AMTX-100 *CF3* drug product is formulated as a water-based, topical cream incorporating a 28-amino acid synthetic polypeptide (AMTX-100) as the active pharmaceutical ingredient (API). AMTX-100 is a chimeric, cell-penetrating, bifunctional nuclear transport modifier (NTM), that is engineered to modulate nuclear transport of transcription factors (NF- $\kappa$ B, NFAT, AP-1 and STAT1) involved in activation of gene expression of key mediators of inflammation (TNF $\alpha$ , IL-1 $\beta$ , IL-6, IL-17, MCP-1, etc.) and metabolic syndrome (ChREBP and SREBP) by importin  $\alpha/\beta$  complex and importin  $\beta$ ,

respectively. This further leads to a reduction in pro-inflammatory cytokine/chemokine production and carbohydrate and lipid metabolic products.

Several nonclinical safety studies have been conducted with AMTX-100 and AMTX-100 *CF* to evaluate its toxicological profile and additional studies are currently ongoing. Substantial scientific literature is also available on the anti-inflammatory mechanisms of AMTX-100.

The current study is designed to evaluate the safety and tolerability of open-label topically applied AMTX-100 *CF3* (in 1.1% concentration) and to evaluate the safety and efficacy of topically applied AMTX-100 *CF3* (1.1% w/w) in adult patients with mild to moderate AD.

■ [REDACTED] ■ [REDACTED]

[REDACTED]

[REDACTED]

[REDACTED]

[REDACTED]

[REDACTED]

### 1.3.1 AMTX-100 PRE-CLINICAL STUDIES

[figure not shown]
Several nonclinical safety studies have been conducted with AMTX-100 and AMTX-100 *CF* to evaluate its toxicological profile; additional studies are currently ongoing. Substantial scientific literature is also available on the anti-inflammatory mechanisms of AMTX-100.

## 1.4 STUDY DESIGN RATIONALE

Following substantial prior pre-clinical studies, to further evaluate the safety and efficacy of different doses of AMTX-100 drug product in improving symptoms associated with mild to moderate atopic dermatitis, Amytrx Therapeutics, Inc (Sponsor) plans to conduct this Two-part, Phase I/II, Multi-center, Double-Blind, Randomized, Vehicle-controlled Study of the Safety and Efficacy of topically applied AMTX-100 *CF* in adult patients with Mild to Moderate Atopic Dermatitis.

## 1.5 RISKS AND BENEFITS, AND PRECAUTIONS TO MINIMIZE RISK

To ensure that AMTX-100 (active pharmaceutical ingredient) and AMTX-100 *CF* (topical formulation) are safe as a human therapeutic agent, below safety studies were conducted. All toxicology studies of AMTX-100 *CF* and AMTX-100 are listed in [Table 1-1](#), including information on the Good Lab Practices (GLP) status and testing facility.

[REDACTED]

[REDACTED]

[REDACTED]

All these study results indicate that AMTX-100 *CF* topical formulation is safe for clinical application. Based on the current data, AMTX-100 may show anti-inflammatory mechanism of action and improve symptoms associated with atopic dermatitis.

**1.5.1 ALLERGIC REACTION**

Pre-clinical studies have not shown that AMTX-100 or AMTX-100 *CF* topical administration might be associated with allergic reactions, however in this first in human study sufficient surveillance of any adverse events and administration reactions will be conducted.

**1.5.2 PREGNANCY**

Risks to unborn babies are unknown at this time, thus pregnant females will be excluded from this study. Females of childbearing potential must have a negative pregnancy test prior to enrollment and must agree to use appropriate birth control methods throughout the study duration (excluding women who are not of childbearing potential).

**1.5.3 VENIPUNCTURE FOR BLOOD SAMPLING**

Venipuncture for blood sample collection carries a minimal risk of minor discomfort and the possibility of minor bruising at the site of the needle puncture and, rarely, the possibility of infection at the needle puncture site.

**1.5.4 UNKNOWN RISKS**

As with all research there is the remote possibility of risks that are unknown or that cannot be foreseen based on current information.

[REDACTED]

[REDACTED]

[REDACTED]

[REDACTED]

## 2 STUDY OBJECTIVES

This is an adaptive, Phase I/II study in 2 parts: Part 1 (Maximum Tolerable Dose (MTD) Finding by maximum BSA percentage treated) and Part 2 (evaluating efficacy of AMTX-100 *CF3* versus placebo (vehicle)).

### Phase I (Part 1) Objectives:

- The primary objective of Part 1 of this study is to determine the MTD of topically applied AMTX-100 *CF* (in 1.1% w/w concentration) in adult patients with mild to moderate Atopic Dermatitis (AD) while escalating the treatable BSA involved in sequential cohorts.
- The secondary objective of Part 1 of this study is to evaluate the safety, tolerability and efficacy of topically applied AMTX-100 *CF* (in 1.1% w/w concentration) in improving symptoms associated with mild to moderate Atopic Dermatitis in adults.

### Phase II (Part 2) Objectives:

- The primary objective of Part 2 of this study is to evaluate efficacy of AMTX-100 *CF3* 1.1% w/w versus placebo (0 % w/w)(Vehicle).
- The secondary objective of Part 2 of this study is to evaluate the safety and tolerability of AMTX-100 *CF3* 1.1% w/w compared to placebo (0 % w/w).

[REDACTED]

### 3 STUDY DESIGN

This is an adaptive, Phase I/II study in 2 parts: Part 1 (Maximum Tolerable Dose (MTD) Finding by maximum BSA percentage treated) and Part 2 (evaluating efficacy of AMTX-100 CF3 1.1% w/w concentration versus placebo (vehicle)).

#### 3.1 PHASE I (PART 1) STUDY DESIGN

Part 1 of this study is an open-label, dose escalation study of the safety and tolerability of topically applied AMTX-100 CF in adult patients with mild to moderate AD. Part I of this study is designed to determine the MTD of AMTX-100 CF (1.1% w/w concentration) for the highest treated percentage of the BSA affected with AD. The MTD is defined as 1 cohort dose level below the dose, in which dose limiting toxicities (DLTs) as defined below were observed.

In total, five (5) cohort dose levels will be tested sequentially by escalating AMTX-100 CF 1.1% to higher percentage of BSA affected with AD at each cohort. Each enrolled subject will receive the assigned dose of Open-label AMTX-100 CF 1.1% w/w to be applied twice daily to all treatable lesions of AD (excluding the scalp, face, eyes, eyelids, neck, hands, palms, feet, groin, genitals or in the axillae) for 7 consecutive days (14 applications in total), regardless of whether the lesions become clinically clear during the 7 days treatment period.

[REDACTED]

[REDACTED]

[REDACTED]

[REDACTED]

[REDACTED]

[REDACTED]

[REDACTED]

For schematics of the cohort escalation and design of Phase I (Part 1) of the study, see text [Figure 3-1](#) and [Figure 3-2](#).

[REDACTED]

[REDACTED]

[REDACTED]

[REDACTED]

[REDACTED]

### 3.2 PHASE I (PART 1) STUDY VISITS

[REDACTED]

[REDACTED]

[REDACTED]

[REDACTED]

[figure not shown]
[REDACTED]

[REDACTED]

[REDACTED]

[REDACTED]

Assuming no DLTs occur at any cohorts, in Part 2 (Phase II) of the study, 1.1% w/w dose concentration of AMTX-100 *CF3* will be further evaluated for the safety and efficacy, compared to placebo (vehicle), in adult patients with mild to moderate AD, with up to 30% treatable BSA involvement.

[figure not shown]
[figure not shown]
[figure not shown]
[figure not shown]

### 3.3 PHASE II (PART 2) STUDY DESIGN

Phase II (Part 2) of this study is a multi-center, double-blind, randomized, vehicle-controlled study of the safety and efficacy of topically applied AMTX-100 *CF3* in adult patients with Mild to Moderate AD. Sixty (60) subjects will be enrolled in 2 groups of AMTX-100 *CF3* and placebo (vehicle). The subjects will be randomized in a 1:1 ratio, thus thirty (30) subjects will be randomized in each group (Group A: Treatment 1.1% w/w of AMTX-100 *CF3*) and Group B: placebo (vehicle 0% w/w)). Each enrolled subject, after screening and randomization, will receive AMTX-100 *CF3* 1.1% w/w or placebo (vehicle) to be applied twice daily to all treatable AD lesions (excluding the scalp, face, eyes, eyelids, hands, palms, feet, groin, genitals or in the axillae) for 28 consecutive days.

The study groups are as follows:

- **Group A:** AMTX-100 *CF3* dose concentration (1.1% w/w), topically applied twice a day for 28 consecutive days to all treatable AD affected areas
- **Group B:** Placebo (Vehicle) (0% w/w), topically applied twice a day for 28 consecutive days to all treatable AD affected areas

[REDACTED]

[REDACTED]

### 3.4 PHASE II (PART 2) STUDY VISITS

[REDACTED]

[REDACTED]

[REDACTED]

[figure not shown]
[REDACTED]

[REDACTED]

[REDACTED]

[REDACTED]

[REDACTED]

## 3.5 STUDY POPULATION

### 3.5.1 NUMBER OF SUBJECTS

**Phase I (Part 1):** Twenty-five (25) subjects will be enrolled in Phase I of the study at up to 5 centers within the USA, including hospitals and freestanding/outpatient dermatology or allergy/immunology clinics. The sample size of 25 subjects (5 subjects per cohort) for phase I of this study is selected on the basis of clinical judgment and not based on statistical power calculation. The number of subjects is deemed adequate to provide clinically meaningful descriptive results consistent with study objectives.

**Phase II (Part 2):** Sixty (60) subjects will be enrolled in Phase II of the study at up to 20 centers within the USA, including hospitals and freestanding/outpatient dermatology or allergy/immunology clinics. The sample size of 60 subjects for Phase II of this study is selected on the basis of clinical judgment and not based on statistical power calculation. The number of subjects is deemed adequate to provide clinically meaningful results consistent with study objectives.

### 3.5.2 SUBJECT SOURCES

Patients referred to and those who are current patients of hospitals and freestanding/outpatient dermatology or allergy/immunology clinics for treatment of atopic dermatitis will be eligible for the study.

### 3.5.3 PHASE I (PART 1) INCLUSION CRITERIA

Subjects are required to meet ALL of the following criteria for enrollment into the Phase I (Part 1) of the study:

1. Male or female subjects who are 18 years or older
2. If female and not infertile (defined below), the subject must agree for the duration of the study to use one of the following forms of contraception 1) systemic hormonal treatment 2) an intrauterine device (IUD) which was implanted at least 2 months prior to screening or 3) "double-barrier" contraception (condom, diaphragm and spermicide are each considered a barrier). Females are considered to be infertile if they are either a) surgically sterile or b) have had spontaneous amenorrhea for at least the last 2 years and at least 2 years after the onset of amenorrhea while not receiving hormone replacement therapy and had a Follicle-Stimulating Hormone (FSH) level greater than 40 mIU/mL and an estradiol level less than 30 pg/mL
3. All fertile female subjects as described above need to have a negative urine pregnancy test at the screening and baseline visits
4. Subject is capable of providing informed consent and is willing to sign the ICF prior to study Screening and agrees to comply with the study protocol requirements
5. Subject is able to apply topical products on all treatable assigned areas by self and/or caregiver (if applicable), per the Investigator

6. Subject is in general good physical/mental health per the Investigator
7. Subject's Total Body Surface Area (BSA) is between 1.5 and 2.1 m^2 per the Mosteller formula
8. The subject has physician confirmed mild to moderate Atopic Dermatitis (AD) defined by the Eichenfield revised criteria of Hannifin and Rajka, for at least 6 months prior to study enrollment
9. Validated Investigator's Global Assessment for Atopic Dermatitis (vIGA-AD™) score of 2 or 3 (mild to moderate) at the screening and baseline visits
10. Subject has Atopic Dermatitis (AD) involvement with eligible treatable percent of the BSA appropriate for topical treatment per the assigned cohort at the screening and baseline visits per below:
  - f. Cohort 1: 3% BSA ≤ AD Affected Area ≤ 6% BSA
  - g. Cohort 2: 6% BSA < AD Affected Area ≤ 12% BSA
  - h. Cohort 3: 12% BSA < AD Affected Area ≤ 24% BSA
  - i. Cohort 4: 24% BSA < AD Affected Area ≤ 48% BSA
  - j. Cohort 5: 48% BSA < AD Affected Area ≤ 70% BSA

### 3.5.4 PHASE I (PART 1) EXCLUSION CRITERIA

Subjects are required to meet NONE of the following criteria for enrollment into the Phase I (Part 1) of the study:

1. Pregnant or lactating females or women who are planning for pregnancy in the next 6 months
2. Women at postpartum for 3 months or less prior to screening
3. Serious medical illnesses such as end-stage renal disease, liver failure or heart failure that, in the opinion of the Investigator may interfere with the conduct of the study
4. Subjects with abnormal vital signs, physical and dermatological exams or clinical laboratory evaluations considered clinically significant by the Principal Investigator, which in the opinion of the PI would significantly interfere with the study conduct
5. Subjects with any concurrent skin condition that could interfere with the evaluation of the treatment areas, as determined by the investigator
6. The subject has a planned major surgical intervention for a pre-existing condition within the duration of the study

7. The subject has a history of drug or alcohol abuse that would impair or risk the subject's full participation in the study, in the opinion of the investigator.
8. Participation in a clinical trial within 3 months, or more than two clinical trials within 12 months prior to screening
9. Concurrent or recent use of topical steroids, topical immunosuppressive/immunomodulative drugs, topical vitamin D3 derivative, topical retinoids, anthralin, coal tar (except when used as shampoo) or salicylic acid within 14 days of the baseline visit
10. The subject has severe AD as determined by vIGA-AD™ score higher than 3
11. The subject cannot avoid systemic treatments (including systemic corticosteroids, immunotherapy, biologics or phototherapy) for AD during the study per the Investigator
12. The subject has previously received any systemic treatments, immunotherapy, biologics or phototherapy for AD within 12 months prior to study enrollment
13. Current or expected use of prohibited medications as described in [Section 7](#), unless approved by the study Medical Monitor
14. The subject has concurrent contact dermatitis; or history of anaphylactic reaction

### **3.5.5 PHASE II (PART 2) INCLUSION CRITERIA**

Subjects are required to meet ALL of the following criteria for randomization into the Phase II (Part 2) of the study:

1. Male or female subjects who are 18 years or older.
2. If female and not infertile (defined below), the subject must agree for the duration of the study to use one of the following forms of contraception 1) systemic hormonal treatment 2) an intrauterine device (IUD) which was implanted at least 2 months prior to screening or 3) "double-barrier" contraception (condom, diaphragm and spermicide are each considered a barrier). Females are considered to be infertile if they are either a) surgically sterile or b) have had spontaneous amenorrhea for at least the last 2 years and at least 2 years after the onset of amenorrhea while not receiving hormone replacement therapy.
3. All fertile female subjects as described above need to have a negative urine pregnancy test at the screening and baseline visits.
4. Subject is capable of providing informed consent and is willing to sign the ICF prior to study Screening and agrees to comply with the study protocol requirements.
5. Subject is able to apply topical products on all the treatable areas by self and/or caregiver (if applicable), per the Investigator.
6. Subject is willing and able to comply with all clinic visits and study-related procedures.
7. Subject is able to understand and complete study-related questionnaires.

8. The subject has physician confirmed mild to moderate Atopic Dermatitis (AD) defined by the Eichenfield revised criteria of Hannifin and Rajka, for at least 6 months prior to study enrollment.
9. Validated Investigator's Global Assessment for Atopic Dermatitis (vIGA-AD™) score of 2 or 3 (mild to moderate) at the screening and baseline visits.
10. Eczema Area and Severity Index (EASI) score lower than 23 at the screening and baseline visits
11. Subject has Atopic Dermatitis (AD) involvement between 5% and 30% treatable BSA (excluding the scalp, face, eyes, eyelids, hands, palms, feet, groin, genitals or in the axillae) appropriate for topical treatment at the screening and baseline visits.

*Note: Calculation of Treatable BSA percentage (% of the total BSA that is AD-involved, excluding the scalp, face, eyes, eyelids, hands, palms, feet, groin, genitals or in the axillae) will be completed by Rule of Nines method:*

- *Where values of 9% or 18% of BSA are assigned to specific regions in the adult subject (head and neck [9%], anterior trunk [18%], back [18%], upper limbs [18%], lower limbs [36%], and genitals [1%])*

12. Subjects must be applying an additive-free, basic, bland emollient twice-daily for at least 1 week immediately before the baseline visit (Visit 2, Day 0), and to be continued throughout the study.

*Note: The additive-free, basic, bland emollients should be applied no earlier than 1 hour before or 1 hour after the administration of the study treatment.*

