Phase I (Part 1) Subject Eligibility Inclusion Criteria: Subjects are required to meet ALL of the following criteria for enrollment into the Phase I (Part 1) of the study:	

 
1. Male or female subjects who are 18 years or older
 
2. If female and not infertile (defined below), the subject must agree for the duration of the study to use one of the following forms of contraception 1) systemic hormonal treatment 2) an intrauterine device (IUD) which was implanted at least 2 months prior to screening or 3) "double-barrier" contraception (condom, diaphragm and spermicide are each considered a barrier). Females are considered to be infertile if they are either a) surgically sterile or b) have had spontaneous amenorrhea for at least the last 2 years and at least 2 years after the onset of amenorrhea while not receiving hormone replacement therapy and had a Follicle-Stimulating Hormone (FSH) level greater than 40 mIU/mL and an estradiol level less than 30 pg/mL
 
3. All fertile female subjects as described above need to have a negative urine pregnancy test at the screening and baseline visits
 
4. Subject is capable of providing informed consent and is willing to sign the ICF prior to study Screening and agrees to comply with the study protocol requirements
 
5. Subject is able to apply topical products on all treatable assigned areas by self and/or caregiver (if applicable), per the Investigator
 
6. Subject is in general good physical/mental health per the Investigator
 
7. Subject's Total Body Surface Area (BSA) is between 1.5 and 2.1 m^2 per the Mosteller formula
 
8. The subject has physician confirmed mild to moderate Atopic Dermatitis (AD) defined by the Eichenfield revised criteria of Hannifin and Rajka, for at least 6 months prior to study enrollment
 
9. Validated Investigator's Global Assessment for Atopic Dermatitis (vIGA-AD™) score of 2 or 3 (mild to moderate) at the screening and baseline visits
 
10. Subject has Atopic Dermatitis (AD) involvement with eligible treatable percent of the BSA appropriate for topical treatment per the assigned cohort at the screening and baseline visits per below: 
 
a. Cohort 1: 3% BSA ≤ AD Affected Area ≤ 6% BSA
 
 
 
	

Name of Sponsor/Company: Amytrx Therapeutics, Inc.	

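### Part 2 counts two years' spontaneous amenorrhoea as infertility without hormone confirmation or a limit to menopause, so its criteria ask for no contraception or pregnancy test in some younger women

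*Protocol*

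**What the plan says.** Both parts of the trial let a woman be classed as infertile in two ways: surgical sterility, or two years of spontaneous amenorrhoea.

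- **Part 1** (Protocol 3.5.3 item 2 and synopsis). The amenorrhoea route also needs laboratory confirmation: "Follicle-Stimulating Hormone (FSH) level greater than 40 mIU/mL and an estradiol level less than 30 pg/mL".
- **Part 2** (Protocol 3.5.5 item 2 and synopsis). The same sentence stops at "at least 2 years after the onset of amenorrhea while not receiving hormone replacement therapy". No hormone threshold follows and nothing replaces it. The only age limit is item 1: "Male or female subjects who are 18 years or older".

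Two obligations in Part 2 hang on this label. Item 2 asks for contraception only from women who are not infertile. Item 3 sets the testing rule: "All fertile female subjects as described above need to have a negative urine pregnancy test at the screening and baseline visits".

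Elsewhere the protocol uses a different term. Section 1.5.2 gives the reason for caution: "Risks to unborn babies are unknown at this time, thus pregnant females will be excluded from this study". It then says: "Females of childbearing potential must have a negative pregnancy test prior to enrollment", and that such women "must agree to use appropriate birth control methods throughout the study duration", with an exemption for women not of childbearing potential. Section 8.9 applies the urine test to the same group. The readable text neither defines the term nor links it to item 2.

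**The concern.** Two years without periods, with no check on cause, does not establish that a woman cannot conceive. Part 1 deals with this by asking for a hormone profile consistent with menopause. Part 2 keeps the clause and removes the check, with no stated reason, while treatment lengthens from 7 days to 28. The treated area is capped lower in Part 2 (30% of body surface against up to 70%), but the readable text does not offer that as a reason either.

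At stake is the safety of a few participants. A woman of reproductive age whose amenorrhoea arose spontaneously from a non-menopausal cause could be randomised with no criterion requiring contraception or a pregnancy test. The sponsor itself says the risk to a fetus is unknown. No efficacy analysis or sample-size argument is affected.

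**Working it through.** No figure in the plan can be reproduced here, so the check sets the texts side by side and then sizes the gap on stated assumptions.

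**Comparing the criteria.** Take a 30-year-old woman, not surgically sterile, off hormone replacement, with more than two years of spontaneous amenorrhoea that is not menopausal.

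| Text | Is she classed as infertile? | Contraception required? | Urine test required? |
|---|---|---|---|
| Part 1 items 2-3 | Only if FSH >40 mIU/mL and estradiol <30 pg/mL | Yes, unless both thresholds are met | Yes, unless both thresholds are met |
| Part 2 items 2-3 | Yes, on history alone | Not required | Not required |
| Section 1.5.2 | Term not defined | Yes, if she counts as of childbearing potential | Yes, on the same condition |
| Section 8.9 | Term not defined | Not addressed | Yes, on the same condition |

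The last two rows protect her only if the site gives childbearing potential its ordinary meaning. If the site reads the term through item 2, she falls outside it. The readable text does not settle which reading applies.

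**How many women.** The inputs are 60 Part 2 subjects randomised 1:1 (Protocol 3.3), an assumed half of them women, and an assumed 0 to 3% of those women with non-menopausal amenorrhoea of two years or more. The documents give neither proportion.

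- Women: 60 x 0.5 = 30.
- Women in the gap: 30 x (0 to 0.03) = 0 to 0.9.
- Of these, on active cream: (0 to 0.9) x 0.5 = 0 to 0.45.

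An exposed pregnancy would be a small fraction of the last figure.

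**Cost of testing every woman who is not surgically sterile.** The further assumption is that 10 to 30% of the 30 women are amenorrhoeic and not surgically sterile; the documents do not give this either.

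- Women newly tested: 30 x (0.10 to 0.30) = 3 to 9.
- Added urine tests: (3 to 9) x 2 visits = 6 to 18 over the whole of Part 2.

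**The case against.** The strongest reply is that the protocol already protects this woman by other routes.

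- The word spontaneous removes induced amenorrhoea, and the clause is probably aimed at menopause. This stands, and it narrows the gap to spontaneous causes other than menopause.
- Part 2 exclusion 1 bars pregnant and lactating women, and exclusion 2 bars those up to three months postpartum. Exclusion 18 lets the investigator turn away anyone with an insufficiently understood condition or at unreasonable risk, and Section 8.4 records ongoing conditions at screening. These are real safeguards. But exclusion 18 and the history are discretionary, none of these provisions requires a test or contraception for her, and an early pregnancy may go unnoticed without a test.
- Section 8.2 sends eligibility to 3.5.5 and 3.5.6, and the exemption in 1.5.2 resembles the fertile/infertile split in item 2. If 1.5.2 defers to item 2, the texts agree, but then they agree on the looser definition.
- The Table 4-2 row labels, visit procedures and laboratory list are blacked out and may add testing. That is possible, so nothing can be said about what will actually be done. The readable criterion still depends on no such result.
- Synopsis and body agree, so the omission may be a deliberate simplification. The remedy allows for that, since it does not make a blood assay routine.

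A reader might go further and infer that items 2-3 contradict Sections 1.5.2 and 8.9. They do not. Item 3 says who must be tested and does not forbid testing anyone else, so a site can satisfy all the texts by testing her. The fault is that the specific rule is silent where the general rule may or may not speak.

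**Conclusion.** The concern holds as a minor safety gap that is cheap to close. Part 2's amenorrhoea clause can label a potentially fertile woman infertile, and its contraception and testing requirements then do not reach her. Sections 1.5.2 and 8.9 might reach her, but they rest on an undefined term.

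Fewer than one woman would be affected: 0 to 0.9 among 60, and 0 to 0.45 on active cream. Those figures rest wholly on the assumed 50% and 0 to 3%, and scale in proportion to each. The textual finding does not depend on them. It would be wrong to conclude that such women will go untested, because the redacted schedule may provide for it and investigators have discretion to act.

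**What to change.** 1. In Part 2 criterion 2 (Protocol 3.5.5 and synopsis), limit the amenorrhoea route to post-menopausal women with no other medical cause. Where menopausal status is in doubt, for example in a younger woman, require the Part 1 thresholds (FSH >40 mIU/mL and estradiol <30 pg/mL). Otherwise treat her as fertile.
2. Apply the criterion 3 urine test at screening and baseline to every woman who is not surgically sterile. This goes beyond Part 1, but it is cheap and uses visits where the test is already done.

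If the sponsor also defines childbearing potential in 1.5.2 and 8.9 by reference to criterion 2, that should follow step 1. Done first, it would carry the gap into those sections.

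The cost is wording in the two Part 2 eligibility lists, an occasional hormone assay (avoidable by treating the woman as fertile), and the 6 to 18 urine tests estimated above. The downside is that a few post-menopausal women take a urine test they do not need.
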